9.3 Long Term Efficacy Analysis

Assessments to evaluate long term efficacy will be analyzed for the following measures at Week 1, 2, 4, 8, 12, 16, 20, 24, 36, 48, and every 12 weeks thereafter until completion of the study.

- ACR20/50/70 response rates;
- Change from baseline in individual components of ACR response;
- Change from baseline in DAS28 (CRP);
- Change from baseline in DAS28 (ESR);
- Change from baseline in morning stiffness (severity and duration);
- Proportion of subjects achieving LDA and proportion of subjects achieving CR based on DAS28 (CRP), DAS28 (ESR), SDAI, and CDAI criteria;
- Proportion of subjects with no concomitant corticosteroid use (among subjects with corticosteroid use at baseline).

Assessments to evaluate long term efficacy will be analyzed for the following measures at Week 4, 12, 24, 48:

- Change from baseline in EQ-5D-5L;
- Change from baseline in FACIT-F;
- Change from baseline in RA-WIS.
- Change from baseline in SF-36.

Descriptive statistics will be provided for each randomized treatment group sequence as defined in Section 9.1.1. These include the number of observations, mean, standard deviation, 95% CI, median, minimum, Q1, Q3 and maximum for continuous endpoints; and frequencies and percentages with 95% CI using normal approximation for binary endpoints. Plot for each randomized treatment group sequence over time will be provided up to Week 36 and 48.

No missing data imputation will be applied. All efficacy analyses will be based on As Observed (AO) analysis.

Table 10 below provides the overview of the long term efficacy analyses to be performed on different endpoints.

Table 10. Summary of Efficacy Variables and Corresponding Analyses for Long Term Efficacy Analysis

Efficacy Variables	Analysis Method
Binary Endpoints:	

 • ACR20/50/70 response by visit • LDA and CR based on DAS28 (CRP), DAS28 (ESR), SDAI, and CDAI criteria by visit • Proportion of subjects with no concomitant corticosteroid use (among subjects with corticosteroid use at baseline) 	
 • Point estimate and 95% CI of the response rate for each randomized treatment group sequence • Plot for each randomized treatment group sequence over time • Imputation: AO • Analysis Set: FAS
Continuous Endpoints:	

 • Change from baseline in individual ACR components by visit • Change from baseline in DAS28 (CRP) by visit • Change from baseline in DAS28 (ESR) by visit • Change from baseline in morning stiffness (severity and duration) by visit • Change from baseline in EQ-5D-5L by visit • Change from baseline in FACIT-F; • Change from baseline in RA-WIS. • Change from baseline in SF-36 by visit 	
 • Point estimate, 95% CI of mean change from baseline together with SD, Min, Q1, Median, Q3 and Max for each randomized treatment group sequence • Plot for each randomized treatment group sequence over time • Imputation: AO • Analysis Set: FAS

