**5.4 Removal of Subjects from Therapy or Assessment****5.4.1 Discontinuation of Individual Subjects**

Subjects can request to be discontinued from participation in the study at any time for any reason, including but not limited to disease progression or lack of response to treatment. The Investigator may discontinue any subject's participation for any reason, including an AE, safety concerns, lack of efficacy, or failure to comply with the protocol. See Section 6.1.7 for toxicity management criteria.

Subjects will be withdrawn from the study immediately if any of the following occur:

- Clinically significant abnormal laboratory results or AEs, which rule out continuation of the study drug, as determined by the Investigator or the AbbVie TA MD.
- Serious infections (e.g., sepsis) which cannot be adequately controlled within 2 weeks by anti-infective treatment or would put the subject at risk for continued participation in the trial as determined by the Investigator.
- The Investigator believes it is in the best interest of the subject.
- The subject requests withdrawal from the study.
- Inclusion or exclusion criteria violation was noted after the subject started study drug, when continuation of the study drug would place the subject at risk as determined by the AbbVie TA MD.
- Introduction of prohibited medications or dosages when continuation of the study drug would place the subject at risk, as determined by the AbbVie TA MD.
- Subject is non-compliant with TB prophylaxis (if applicable) or develops active TB at any time during the study.
- The subject becomes pregnant while on study drug.
- Malignancy, except for localized NMSC or carcinoma in situ of the cervix.
- Subject is significantly non-compliant with study procedures which would put the subject at risk for continued participation in the trial as determined by the Investigator.

- Subject develops a gastrointestinal perforation.
- Starting at Week 24, at least 20% improvement in BOTH TJC and SJC compared to baseline is required to remain in the study. Anyone who does not fulfill this criterion at 2 consecutive visits (starting at Week 24) must be discontinued from the study.
- If a subject is unblinded in Period 1, as summarized in Section [5.5.5](#).

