If a subject prematurely discontinues study drug treatment and study participation (withdrawal of informed consent), the procedures outlined for the Premature Discontinuation visit (PD Visit) should be completed as soon as possible, preferably within 2 weeks. A 30-day follow-up visit/phone call may occur for subjects who prematurely discontinued from study drug and study participation to determine the status of any upadacitinib ongoing AEs/SAEs or the occurrence of any new AEs/SAEs (refer to Section [5.1](#) regarding Follow-Up Visit). Subjects who discontinue the study prematurely after randomization will not be replaced.

All attempts must be made to determine the date of the last study drug dose and the primary reason for discontinuation of study participation. The information will be recorded on the appropriate eCRF page. However, these procedures should not interfere with the initiation of any new treatments or therapeutic modalities that the Investigator feels are necessary to treat the subject's condition. Following discontinuation of study drug, the subject will be treated in accordance with the Investigator's best clinical judgment.

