5.2 Analysis Windows

Definition of Study Days (Days Relative to the First Dose of Study Drug)

Study Days are calculated for each collection date relative to the date of the first dose of study drug. It is defined as the number of days between the date of the first dose of study drug and the collection date. Study days are negative values when the collection date of interest is prior to the first study drug dose date. Study days are positive values when the collection date of interest is on or after the first study drug dose date. The day of the

first dose of study drug is defined as Study Day 1, while the day prior to the first study drug dose is defined as Study Day –1 (there is no Study Day 0). Study days are used to map actual study visits to the protocol-specified study visits.

Definition of Analysis Windows

The following rules will be applied to assign actual subject visits to protocol-specified visits. For each protocol-specified study visit, a target study day will be identified to represent the corresponding visit along with a window around the target day. Windows will be selected in a non-overlapping fashion so that a collection date does not fall into multiple visit windows. If a subject has two or more actual visits in one visit window, the visit closest to the target day will be used for analysis. If two visits are equidistant from the target day, then the later visit will be used for analysis.

The visit window and the target study day for each protocol-specified visit in Period 1 are displayed in [Table 4](#) and [Table 6](#) (depending on the different visit schedules of different endpoints). Visit windows for protocol-specified visits in Period 2 are defined similarly.

Table 4. Analysis Windows for Efficacy Analysis for Period 1 (for ACR Components and Morning Stiffness)

Protocol Specified Visit Week	Lower Bound	Target Day	Upper Bound
Baseline	–99	1 ^a	1
1	2	8	11
2	12	15	22
4	23	29	43
8	44	57	71
12	72	85	min (99, first dose date of Period 2)

a. Day of first dose of study drug.

Table 5. Analysis Windows for Safety Analysis for Period 1 (for Labs and Vital Signs)

Protocol Specified Visit Week	Lower Bound	Target Day	Upper Bound
Baseline	-99	1 ^a	1
2	2	15	22
4	23	29	43
8	44	57	71
12	72	85	min (99, first dose date of Period 2)

a. Day of first dose of study drug.

Table 6. Analysis Windows for Efficacy Analysis for Period 1 (for EQ-5D-5L, SF-36, FACIT-F and RA-WIS)

Protocol Specified Visit Week	Lower Bound	Target Day	Upper Bound

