9.1.2 Definition of Missing Data Imputation

Non-Responder Imputation (NRI) Approach

The NRI approach will categorize any subject who has missing value for categorical variables at a specific visit as non-responder for that visit. In addition, subjects who prematurely discontinue from study drug will be considered as non-responders for all subsequent visits after discontinuation.

Observed Cases (OC)

The OC analysis will not impute values for missing evaluations, and thus a subject who does not have an evaluation on a scheduled visit will be excluded from the OC analysis for that visit. In addition, the OC will not use values after premature discontinuation of study drug. This sensitivity analysis will only be applied to the analysis in Period 1.

As Observed (AO)

The AO analysis will not impute values for missing evaluations, and thus a subject who does not have an evaluation on a scheduled visit will be excluded from the AO analysis for that visit. Regardless of treatment switching or premature discontinuation of study drug, all observed data will be used in the analysis. The AO analysis will be applied to long term efficacy analysis.

Mixed Effect Model Repeat Measurement (MMRM)

The repeated measure analysis will be conducted using mixed model including observed measurements at all visits. The mixed model includes the categorical fixed effects of treatment, visit and treatment-by-visit interaction, main stratification factors at randomization, and the continuous fixed covariates of baseline measurement. An unstructured variance covariance matrix will be used. The parameter estimations is based on assumption of data being missing at random and using the method of restrictive maximum likelihood (REML).

Multiple Imputation (MI)

The MI analysis will impute missing data multiple times under appropriate random variation and thus generate multiple imputed "pseudo-complete" datasets. Results will be aggregated across the multiple imputed datasets, overcoming drawbacks of the single imputation methods.

9.2 Efficacy Analysis for Period 1

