9.4 Efficacy Variables Definitions and Conventions

9.4.1 ACR Criteria

ACR criteria are a commonly used standard criteria set mentioned in the guidance of American College of Rheumatology to evaluate the effectiveness of investigation drug in RA clinical trials. It is a composite measurement calculated based on the improvement over a set of core measurements.

ACR20 is defined as at least 20% improvement (compared to baseline values) in tender and swollen joint counts and at least 20% improvement in 3 of the remaining 5 core set measures (subject global assessment of pain, subject global assessment of disease activity, physician global assessment of disease activity, subject assessment of physical function and acute phase reactant hsCRP).

ACR50 and ACR70 are similarly defined with at least 50% and 70% improvement, respectively.

A subject will be classified as an ACR20 (ACR50, ACR70) responder, if the following conditions are met:

1. $\geq 20\%$ (50% , 70%) improvement from baseline in tender joint count (TJC68) and
2. $\geq 20\%$ (50% , 70%) improvement from baseline in swollen joint count (SJC66) and
3. $\geq 20\%$ (50% , 70%) improvement from baseline in at least 3 of the following 5:
 - patient's assessment of pain
 - patient's global assessment of disease activity (PGA)
 - physician's global assessment of disease activity (PhGA)
 - patient's self-assessment of physical function (i.e., measured by Health Assessment Questionnaire (HAQ-DI score)
 - Acute-phase reactant value CRP

There are seven components to be evaluated to define an ACR response. Missing values for each component can occur due to a missed visit or due to dropout from the study.

Depending on the pattern of the missing components, ACR responses may be or may not be determined using observed values only.

Upadacitinib
M14-663 – Statistical Analysis Plan
Version 1.0 – 31 Aug 2017

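### Long-term ACR20/50/70 is summarised As Observed only, so subjects removed under the 20% joint rule leave the denominator (on schedule, from Week 48), and no planned rate keeps them as non-responders

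*SAP*

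**What the plan says.** **Method.** SAP 9.3 states: "No missing data imputation will be applied. All efficacy analyses will be based on As Observed (AO) analysis". Table 10 repeats As Observed (AO) for the binary endpoints, by the six randomized sequences, on the FAS. Under the AO definition in SAP 9.1.2 there is no imputation, "thus a subject who does not have an evaluation on a scheduled visit will be excluded from the AO analysis for that visit".

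**Removal rule.** Protocol 5.4.1 requires at least 20% improvement in both joint counts from Week 24 and adds: "Anyone who does not fulfill this criterion at 2 consecutive visits (starting at Week 24) must be discontinued from the study".

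**Endpoint.** SAP 9.4.1: "ACR20 is defined as at least 20% improvement (compared to baseline values) in tender and swollen joint counts", plus three of five other measures. ACR50 and ACR70 raise the same thresholds.

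**Non-responder imputation (NRI).** SAP 9.1.2 already defines it. It would "categorize any subject who has missing value for categorical variables at a specific visit as non-responder for that visit", and "subjects who prematurely discontinue from study drug will be considered as non-responders for all subsequent visits after discontinuation". Table 9 assigns NRI to Period 1 only. Protocol 8.1.4.2 names no imputation method for the long-term summary.

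**After removal.** Protocol 5.4.1 asks that "the procedures outlined for the Premature Discontinuation visit (PD Visit) should be completed as soon as possible, preferably within 2 weeks". The 30-day follow-up (Protocol 5.1) covers adverse events, vital signs and laboratory tests, not joint counts.

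**The concern.** The criterion for removal is a mandatory part of the endpoint. A subject who triggers the rule is, by definition, an ACR non-responder at both trigger visits. AO counts that subject correctly at those two visits and at none afterwards. This differs from ordinary dropout, because the protocol itself selects on the outcome.

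Long-term efficacy is a Period 2 objective (Protocol 4.0), and SAP 9.3 plots the sequences over time up to Weeks 36 and 48. An AO curve can rise between those two visits because known non-responders have left, with no subject having improved. A reader of the planned tables would have no companion rate to show how much of a rise has that source.

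**Working it through.** The plan states no figure for this effect, so there is none to reproduce. The check covers timing, the visit window, the size of the mechanism, and what other tables would show.

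**1. First visit affected.** Period 2 visits are at Weeks 16, 20, 24, 36, 48 and every 12 weeks after. The earliest scheduled failing pair is Weeks 24 and 36, so the first scheduled visit after removal is Week 48. The notes to Protocol Table 4 allow any procedure at an unscheduled visit; if such a visit counted as one of the two, removal could come earlier.

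**2. Does the premature discontinuation (PD) visit supply a Week 48 value?** SAP 5.2 says only: "Visit windows for protocol-specified visits in Period 2 are defined similarly". The Period 1 bounds in SAP Table 4 are midpoints between target days (7 × week + 1):
- (8 + 15)/2 = 11.5, bound 11
- (15 + 29)/2 = 22, bound 22
- (29 + 57)/2 = 43, bound 43
- (57 + 85)/2 = 71, bound 71

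Carrying that rule into Period 2 (an assumption):
- Week 36 target: 7 × 36 + 1 = Day 253. Week 48 target: 7 × 48 + 1 = Day 337.
- Upper bound for Week 36: (253 + 337)/2 = Day 295.
- Latest Week 36 visit, with the ±7-day window: Day 260.
- PD visit 14 days later: Day 274, which is 21 days inside the Week 36 window.

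To fall in the Week 48 window, the PD visit would have to come at least 296 − 260 = 36 days after that latest visit. Two weeks is a preference, not a limit, so this is possible but is not what the protocol asks for.

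**3. Size.** Let N subjects be due at a visit, x of them responders, and r removed as non-responders, with nothing else missing.
- Rate keeping the removed as non-responders: x/N
- AO rate: x/(N − r)
- Ratio: N/(N − r), never below 1

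Neither r nor x is in the documents, so the counts below are assumed. N = 16 and N = 48 are the planned sequence sizes; 33/48 is close to the 68% planning rate for 15 mg in SAP 4.3.

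| N | x | x/N | r | AO rate |
|---|---|---|---|---|
| 16 | 10 | 62.5% | 1 | 10/15 = 66.7% |
| 16 | 10 | 62.5% | 2 | 10/14 = 71.4% |
| 16 | 10 | 62.5% | 3 | 10/13 = 76.9% |
| 48 | 33 | 68.8% | 2 | 33/46 = 71.7% |
| 48 | 33 | 68.8% | 4 | 33/44 = 75.0% |
| 48 | 33 | 68.8% | 6 | 33/42 = 78.6% |

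**4. What other planned tables show.** SAP 7.0 lists lack of efficacy among the Period 2 reasons for stopping study drug. That gives an efficacy-related dropout count, but by pooled actual dose, not by sequence or visit, and not specific to the joint rule. AO counts per visit do not separate removed subjects from those who have not yet reached the visit.

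**The case against.** The strongest reply is that AO was chosen and defined on purpose for a descriptive, untested summary, so leaving NRI out is neither an error nor a contradiction. That is fair as far as it goes. But in a descriptive analysis the reported rate is itself the result, and here it is conditioned on the protocol's own efficacy rule.

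Four stronger readings might be inferred, and the documents do not support them.

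- *The non-responder rate can never be recovered.* Too strong. Once all subjects have passed Week 48, it can be approximated there as AO responders divided by the FAS count, provided that count is shown for all six sequences. It cannot at an earlier regulatory cut (SAP 4.4 allows further unblinded analyses) or for late visits that not all subjects could reach.
- *The reports would say nothing about efficacy dropout.* The lack-of-efficacy category does give something by dose, within the limits above.
- *Every poor responder is filtered out.* Removal needs two consecutive failures. Subjects who fail once, or who miss ACR20 on the other five measures, stay as observed non-responders.
- *The dose comparison is distorted in a known direction, or remission and low disease activity are affected in the same way.* The direction between doses cannot be determined without removal rates. The disease-activity indices use 28-joint counts, so failing the 66/68-joint rule does not by itself establish non-response on them.

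The reply also limits the remedy. An all-FAS denominator would count someone who left on placebo, never having received upadacitinib, as a failure of a placebo-to-upadacitinib sequence. The Period 2 objective concerns subjects who completed Period 1. In a planned sequence of 16, one subject is 1/16 = 6.25%.

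**Conclusion.** The point holds as a reporting gap that should be closed. At visits after removal, AO ACR20/50/70 rates equal or exceed a rate that keeps joint-rule removals as non-responders. The factor is N/(N − r) if nothing else is missing, and the size is unknown. That Week 48 is the first visit affected rests on the scheduled visits, on midpoint Period 2 windows, and on PD visits within the preferred two weeks. The trigger visits themselves are counted correctly, and the Week 12 conclusion is unaffected.

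There is also a wording mismatch. SAP 4.2 says study drug is discontinued under the joint rule, whereas Protocol 5.4.1 and note j to SAP Table 3 say the subject is discontinued from the study. Since AO uses data observed after study drug stops, SAP 4.2 could be read as implying continued follow-up. Neither document schedules visits off drug, so that reading is not supported, but the passages must be reconciled.

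**What to change.** Keep AO. Add to SAP 9.3 and Table 10:

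- A supplementary NRI analysis of ACR20/50/70 for visits after Week 12, by randomized treatment group sequence and visit.
- Denominator: FAS subjects who entered Period 2 and whose target day for the visit falls on or before the data cut or, at the final analysis, a common date closing Period 2. The same date rule applies to ongoing and discontinued subjects.
- Subjects who discontinued prematurely are non-responders at all later visits.
- Beside it, by sequence and visit: the number evaluable under AO and the cumulative number removed under the joint rule.

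The date rule is needed because the NRI text in SAP 9.1.2 treats any missing value as non-response. Applied literally at a data cut, it would fail ongoing subjects who have not yet reached the visit.

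Reconcile SAP 4.2 with Protocol 5.4.1 and note j to SAP Table 3.

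The cost is one more set of descriptive tables, a closing date to define, and a removal flag derived from the joint counts, since the discontinuation reasons do not identify the rule. The added rates will equal or fall below AO on the same subjects, and they also count adverse-event and consent dropouts as non-response. They therefore belong beside AO, not in place of it; the removal count lets a reader separate the causes.

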9.4 Efficacy Variables Definitions and Conventions

9.4.1 ACR Criteria

ACR criteria are a commonly used standard criteria set mentioned in the guidance of American College of Rheumatology to evaluate the effectiveness of investigation drug in RA clinical trials. It is a composite measurement calculated based on the improvement over a set of core measurements.

ACR20 is defined as at least 20% improvement (compared to baseline values) in tender and swollen joint counts and at least 20% improvement in 3 of the remaining 5 core set measures (subject global assessment of pain, subject global assessment of disease activity, physician global assessment of disease activity, subject assessment of physical function and acute phase reactant hsCRP).

ACR50 and ACR70 are similarly defined with at least 50% and 70% improvement, respectively.

A subject will be classified as an ACR20 (ACR50, ACR70) responder, if the following conditions are met:

1. $\geq 20\%$ (50% , 70%) improvement from baseline in tender joint count (TJC68) and
2. $\geq 20\%$ (50% , 70%) improvement from baseline in swollen joint count (SJC66) and
3. $\geq 20\%$ (50% , 70%) improvement from baseline in at least 3 of the following 5:
 - patient's assessment of pain
 - patient's global assessment of disease activity (PGA)
 - physician's global assessment of disease activity (PhGA)
 - patient's self-assessment of physical function (i.e., measured by Health Assessment Questionnaire (HAQ-DI score)
 - Acute-phase reactant value CRP

There are seven components to be evaluated to define an ACR response. Missing values for each component can occur due to a missed visit or due to dropout from the study.

Depending on the pattern of the missing components, ACR responses may be or may not be determined using observed values only.

Upadacitinib
M14-663 – Statistical Analysis Plan
Version 1.0 – 31 Aug 2017

